9.4.3. Exploratory Endpoints

Exploratory endpoint analyses will be detailed in the SAP.

If appropriate, subgroup or covariate-adjusted analyses may be performed. These subgroups/covariates may include baseline demographics and other characteristics.

9.4.4. Other Analyses

Participant Medical Information Prior to, During and After the Study (Real-world Data, in US Participants Only)

The exploratory analyses that may be conducted using the real-world data will be detailed in a SAP and results may, partially, be reported separately from the VAC31518 Clinical Study Report(s).

Medical Resource Utilization Analyses

Medical resource utilization will be descriptively summarized by intervention group.

9.5. Immunogenicity Analyses

For the double-blind phase, no formal statistical testing of the immunogenicity data is planned. All immunogenicity analyses will be performed on the PPI set. Key tables might be repeated for the FAS (including samples that are excluded from the PPI analysis). For the open-label phase and passive follow-up phase, no statistical testing of the immunogenicity data is planned. All details regarding the analysis and will be described in the SAP.

9.5.1. Immunogenicity Subset

No formal hypothesis on immunogenicity will be tested. Descriptive statistics (eg, geometric mean and 95% confidence interval for the neutralization assay and ELISA) will be calculated for continuous immunologic parameters at all timepoints. Geometric mean fold rises from baseline and corresponding 95% confidence intervals might additionally be calculated. Baseline is considered as the last available assessment before vaccination. Graphical representations of immunologic parameters will be made as applicable.

The impact of baseline factors on the humoral responses will be explored graphically or via descriptive statistics. In addition, in a subset of 400 participants (the Immunogenicity Subset; ~200 from the active group, ~200 from the placebo group), humoral immunogenicity samples are taken on more occasions.

9.5.2. Correlates of Risk

If VE is demonstrated, correlates of risk will be explored. Details with appropriate methods will then be provided in a separate analysis plan.

9.6. Safety Analysis

No formal statistical testing of safety data is planned. Safety data according to the vaccination received and based on the FAS will be analyzed descriptively. The analysis of solicited and unsolicited AEs will be restricted to a subset of the FAS (ie, the Safety Subset).

For SAEs, AESIs, and MAAEs the full FAS is considered. New onset of chronic diseases will be collected as part of the MAAEs.

Subanalyses (descriptive) will be performed on participants with stable/well-controlled HIV infection to evaluate the effect of the vaccine on HIV RNA viral load and CD4 cell count.

Safety endpoints following the open-label vaccination and following the booster vaccination will be descriptively summarized. Pooled safety analyses with other studies may also be performed.

Adverse Events (Solicited and Unsolicited) (Double-blind Phase)

The verbatim terms used in the eCRF by investigators to identify AEs will be coded using the Medical Dictionary for Regulatory Activities (MedDRA). All Reported AEs with onset during the active vaccination phase (ie, AEs occurring after vaccination up to 28 days after each vaccination), and all SAEs/MAAEs/AESIs will be included in the analysis. (S)AEs caused by molecularly confirmed SARS-CoV-2 infection will be removed at the analysis level from the (S)AE listings and tables and presented separately. For each AE, the percentage of participants who experience at least 1 occurrence of the given event will be summarized by study vaccine group.

Summaries, listings, datasets, or participant narratives may be provided, as appropriate, for those participants who die, who discontinue the study due to an AE or who experience a severe AE, an AESI, or an SAE.

Solicited local (at injection site) and systemic AEs will be summarized descriptively. The number and percentages of participants with at least 1 solicited local (at injection site) or systemic AE will be presented. Solicited AEs shown in the tables and listings will be based on the overall assessment of the investigator. The overall frequencies by vaccine group as well as frequencies according to severity and duration will be described for solicited AEs. Frequencies of unsolicited AEs, separately for all and vaccination-related only, will be presented by System Organ Class and preferred term, while those of solicited AEs will be presented only by preferred term.

Clinical Laboratory Tests

Laboratory data (abnormal or graded, when available) will be listed and/or tabulated by participant and time point.

Vital Signs

For all participants, weight and height (and BMI) at baseline will be summarized using descriptive statistics. Temperature will be measured at each scheduled timepoint and summarized using descriptive statistics. Other vital signs may be measured at the discretion of the investigator. Vital signs abnormalities will be listed.

For COVID-19 cases, temperature will be summarized over time from start of symptoms, using descriptive statistics and/or graphically. For systolic and diastolic blood pressure, heart rate, respiratory rate, oxygen saturation, and pulse oximetry, values and the percentage of participants with values beyond clinically relevant limits will be summarized at each scheduled timepoint. Descriptive statistics will be calculated for changes between COVID-19 Day 29 and COVID-19 Day 3-5.

Physical Examinations

For all participants, physical examinations can be performed at the discretion of the investigator. Physical examination abnormal findings will be listed.

For COVID-19 cases, physical examination findings and the percentage of participants with values beyond clinically relevant limits will be summarized at each scheduled timepoint. Descriptive statistics will be calculated for changes between COVID-19 Day 29 and COVID-19 Day 3-5, if available.

9.7. Analyses of the Open-label Phase

Safety, immunogenicity, and efficacy endpoints following the open-label and/or booster vaccination will be descriptively summarized by the different cohorts (as specified in Section 3) for the different phases (ie, for the active follow-up phase and the passive follow-up phase). Additional analyses may be conducted to support health authority interactions and/or based on public health demand in case of emerging variants.

The statistical methodology, definition of cases for evaluation on the regimen for evaluation as well as data to be included in the data base will be defined in the SAP.

For definitions of the main groups for analysis in the open-label phase, see Section 3.

9.7.1. Immunogenicity Analyses

For the open-label phase, no formal statistical testing of the immunogenicity data is planned.

9.7.2. Immunogenicity Correlates (Correlates Subset)

Correlates for participants who received a booster dose may be explored, similar to the methods as described in Section 9.5 for the double-blind phase.

9.7.3. Safety Analyses

Safety endpoints following the open-label vaccination and following the booster vaccination for both the open-label active phase and the open-label passive follow-up phase will be descriptively summarized. Pooled safety analyses with other studies may also be performed.

9.7.4. Efficacy Analyses

For the analysis of efficacy in the open-label active phase, follow-up time will be expressed on a calendar time scale, and defined as time since a predefined calendar date, eg, study start or time period to start evaluation, to adjust for changing incidence over time.

The analysis will be conducted according to the regimen as received (see Section 3 for the main study cohorts).

Follow-up time (a participant at risk for an event) will begin on the date of administration of the first dose of the vaccine regimen under evaluation, expressed on a calendar time scale as time since

study start/predefined calendar date. Follow-up time and events occurring within 14 days since (last) vaccination may be ignored.

If deemed feasible, efficacy of the booster vaccination may be explored by comparing efficacy data after boosting to data in the absence of booster, on the same primary regimen. Feasibility will be assessed based on data availability as well as adjustments for potential confounding (including, but not limited to age, country and/or site, presence of co-morbidities). Additional factors may be added and prespecified in the SAP.

Efficacy data of the open-label active phase may be compared following a homologous vaccination schedule (Ad26 COV2.S) versus a heterologous vaccination schedule. The duration of protection of the booster vaccinations may be summarized (as early booster versus late booster vaccination).

All details will be described in the SAP.

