7. DISCONTINUATION OF STUDY VACCINATION AND PARTICIPANT DISCONTINUATION/WITHDRAWAL

7.1. Discontinuation of Study Vaccination

Study vaccinations in the double-blind phase will be withheld for the reasons listed below. These participants must not receive any further doses of study vaccine but should remain on study for follow-up with assessments of safety, efficacy, and immunogenicity as indicated in the [Schedules of Activities](#). Additional unscheduled visits may be performed for safety/reactogenicity reasons, if needed. In case of questions, the investigator is encouraged to contact the sponsor.

- Any related AE, worsening of health status or intercurrent illnesses that, in the opinion of the investigator, requires discontinuation from study vaccine
- The participant becomes pregnant
- Unblinding on the participant level that, in the opinion of the sponsor, would compromise the integrity of the data
- Unblinding requested by a study participant in order to receive an authorized/licensed COVID-19 vaccine prior to general unblinding at the time of EUA in the US for the single-dose schedule of Ad26.COV2.S
- Anaphylactic reaction following vaccination, not attributable to causes other than vaccination
- SAE or other potentially life-threatening (Grade 4) event that is determined to be related to study vaccine
- Chronic or recurrent use of systemic corticosteroids and administration of antineoplastic and immunomodulating agents or radiotherapy
- Participant received any experimental medication (including experimental vaccines other than the study vaccine) or received a COVID-19 vaccine or treatment
- Withdrawal of consent to receive further study vaccination
- Participant has a molecularly confirmed SARS-CoV-2 infection based on samples collected within the study (see Section [8.1.2](#))
- Participant previously experienced TTS or HIT.

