9.1. Statistical Hypotheses

Refer to Section 3 for the statistical hypotheses.

The study will have 3 timepoints for analysis:

1. The primary efficacy analysis of the double-blind phase is planned to be performed when all participants have reached the open-label phase/been unblinded. Depending on the operational implementation of unblinding visits, as well as the stage of the pandemic, the analysis may be conducted when a minimum of 90% of the study population have reached the open-label phase/been unblinded.

After the primary analysis, additional analyses to support health authority interactions may be planned, if deemed appropriate.

During the open-label phase, 2 analyses can be performed:

2. The open-label active phase analysis
3. An end-of-study analysis is planned 1 year after a minimum of 90% of the enrolled study population have reached Visit 8 or discontinued earlier and will be conducted upon completion of the last active participant visit. Depending on the timing of approval of Amendment 7 across study sites, the open-label active phase analysis may be combined with the end-of-study analysis. All boosted participants will have at least 6 months safety follow-up.

Additional analyses may be conducted to support health authority interactions and/or based on public health demand in case of emerging variants.

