9.4.1. Primary Endpoint Evaluation for the Double-blind Phase

The double-blind phase of the study is designed to test the primary hypothesis of VE in the PP population: H0: VE $\leq 30\%$ versus H1: VE $> 30\%$ and will be evaluated at a 2.5% 1-sided significance level.

The primary endpoint will evaluate the first occurrence of molecularly confirmed, moderate to severe/critical COVID-19 according to the case definition in Section 8.1.3.1, with onset at least 14 days after the second vaccination (Day 71) with Ad26.COV2.S versus placebo, in the PP population, including all events from both age groups, with and without comorbidities.

Participants included in the seronegative analysis set are those participants with a negative SARS-CoV-2 serology test result at baseline.

The unblinding visit marks for a participant the end of the double-blind phase, and the start of the open-label phase. For a given participant, all data up to the unblinding visit will be incorporated in the analysis of the double-blind phase.

The minimum criteria that may trigger the primary analysis before at least 90% of participants are unblinded is if the prespecified harm boundaries have been crossed.

A successful primary efficacy conclusion will require establishing the hypothesis H1: VE $> 30\%$ for the primary endpoint.

Exact Poisson regression will be used to estimate the VE and associated CI taking into account the follow-up time. To evaluate the primary null hypothesis: H0: VE $\leq 30\%$ versus H1: VE $> 30\%$ for the primary endpoint, 95% 2-sided confidence interval based on Poisson regression model will be used.

The decision rules for harm are detailed in Section 9.4.1.1.

For any case definition to be considered for classification of COVID-19 cases, there needs to be at least one SARS-CoV-2 positive RT-PCR or molecular test result from any available respiratory tract sample (eg, nasal swab sample, sputum sample, throat swab sample, saliva sample) that is confirmed by the central laboratory. It is possible that not all samples can be confirmed at the time of the analysis. Hence, a sensitivity analysis may be performed using all RT-PCR or molecular test result, regardless of the confirmation by the central laboratory.

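### Section 9.7.4 starts 2-dose at-risk time at dose 1 by regimen received, so for participants given both doses while blinded, about 56 nearly case-free days can enter the descriptive 2-dose incidence

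*Protocol*

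**What the plan says.** Section 9.7.4 (Efficacy Analyses, open-label active phase) fixes three things and leaves a fourth optional:

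- Grouping: "The analysis will be conducted according to the regimen as received".
- Start of at-risk time: it "will begin on the date of administration of the first dose of the vaccine regimen under evaluation", placed on a calendar scale.
- Calendar origin: "time since a predefined calendar date, eg, study start or time period to start evaluation".
- Optional exclusion: "Follow-up time and events occurring within 14 days since (last) vaccination may be ignored".

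Among the reasons to withhold vaccination in the double-blind phase, Section 7.1 lists: "Participant has a molecularly confirmed SARS-CoV-2 infection based on samples collected within the study". Such participants get no further dose but stay in follow-up. The parallel list for the open-label phase has no infection item.

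On the boundary between phases, Section 9.4.1 says: "For a given participant, all data up to the unblinding visit will be incorporated in the analysis of the double-blind phase". Section 9.7 says that open-label endpoints will be "descriptively summarized by the different cohorts", and it leaves methodology and the data to be included to the SAP.

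**The concern.** Membership of a 2-dose group defined by doses received is known only once dose 2 has been given. If at-risk time is nevertheless counted from dose 1, the interval between doses is immortal time: a participant had to get through it without a dose-stopping event to be in the group at all. Here one dose-stopping event is the outcome itself. While participants were blinded, a confirmed in-study infection before Day 57 barred dose 2, and with it entry to the 2-dose group.

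Counted this way, the 2-dose group gains person-time with almost no possible cases, and its incidence looks lower even if dose 2 adds nothing. A calendar time scale adjusts for changing background incidence, which is the purpose 9.7.4 gives for it, but not for this selection. At stake is how the open-label cohort summaries are read: part of a lower 2-dose rate could come from the start rule.

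**Working it through.** **Dose interval.** Section 9.2.1 equates Day 71 with 14 days after the second vaccination. Dose 2 is then on Day 71 − 14 = 57, and with dose 1 on Day 1 the interval is 57 − 1 = 56 days. The Amendment 4 history in Appendix 15 also gives Day 57, so the plan's own schedule is reproduced.

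**How the interval becomes nearly case-free.**

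1. By 9.7.4, a participant given two doses is in the 2-dose group, at risk from dose 1.
2. By 7.1, a participant with a confirmed in-study infection while blinded does not get dose 2 and so cannot be in that group by doses received.
3. Hence the 2-dose group has almost no confirmed cases in the 56 days. The interval is nearly, not fully, empty, because serology-only infections (8.1.3.4) can occur there without stopping dose 2.

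**Size.** Assume the same constant, low incidence before and after dose 2 (no added effect), everyone in the group double-dosed while blinded, and follow-up of T days from dose 1. Cases arise over T − 56 days while T days are counted, so

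observed / true incidence = (T − 56) / T, and understatement = 56 / T.

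- T = 365: 56 / 365 = 15.3%.
- T = 421 (one year after dose 2, 56 + 365, which is Visit 8): 56 / 421 = 13.3%.

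**Effect of the optional 14-day exclusion.**

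- After dose 2 only: 1 − (T − 70) / (T − 14). This gives 1 − 295/351 = 16.0% and 1 − 351/407 = 13.8%.
- After each dose: 42 / (T − 28). This gives 42/337 = 12.5% and 42/393 = 10.7%.

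Neither removes the interval; the first slightly increases the understatement.

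**What reduces it.**

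- Incomplete withholding. If 20% of between-dose cases still received dose 2 (assumed), 0.8 × 56 / T = 12.3% and 10.6%.
- Mixed cohort. If a share w of the group was double-dosed while blinded, follow-up is equal and the rest are unaffected, the understatement is w × 56 / T. At w = 0.5 (assumed) it is 7.7% and 6.7%.
- A calendar start after dose 2, or counting only time after unblinding: 0%.

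The follow-up lengths are assumptions. The calculation stops at day 421 because the rule in 9.7.4 covers the open-label active phase, and Amendment 7 replaced active with passive COVID-19 follow-up.

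**The case against.** The strongest reply is about scope. Section 9.7.4 concerns the open-label active phase, 9.4.1 places everything before the unblinding visit in the double-blind analysis, and 9.7 speaks of endpoints following open-label or booster vaccination. On that reading the blinded dose interval is never counted. Section 9.7 also defers the data to be included to the SAP, and 9.7.4 allows a later evaluation period as the origin.

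Much of this stands: it gives a credible route to no bias, and it is why the size is a ceiling. It does not settle the matter. Assigning data to the double-blind analysis does not bar their reuse. The start rule itself is stated, not deferred, and for anyone first vaccinated while blinded it names a date before unblinding. Study start is an expressly permitted origin. An SAP that follows the rule literally inherits the problem, and one that corrects it departs from the protocol text.

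Three further objections also stand:

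- A reader might infer that between-dose cases necessarily pass to a 1-dose cohort and widen the contrast. That depends on the cohort definitions in Section 3, which are not available here. Single-dose recipients could also later be boosted.
- Section 9.7.4 names no 2-dose versus 1-dose efficacy comparison. The contrasts it lists (boosted versus not boosted, homologous versus heterologous, early versus late booster) are all optional. Any side-by-side reading comes from the general sentence in 9.7.
- The ratio 56 / T describes a crude rate, and a calendar-time analysis need not give the same figure. Section 9.2.1 assumes falling incidence, so the constant-incidence figures are illustrations, not predictions.

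**Conclusion.** The point holds as a defect in a stated rule, with limited reach. Applied literally, 9.7.4 lets 56 nearly case-free days into the 2-dose group for participants who received both doses while blinded. The resulting understatement of the descriptive 2-dose incidence is up to about 15% at 365 days and 13% at day 421 from dose 1.

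Those figures rest on five conditions: a calendar date before dose 2, pre-unblinding time being counted, a cohort double-dosed wholly while blinded, near-complete withholding after infection, and constant incidence with no added effect of dose 2. Including people given dose 2 open-label lowers them. Either of the two restrictive readings, a start after dose 2 or post-unblinding time only, takes them to zero.

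A reader might go further and conclude that the trial's efficacy result is biased. The documents do not support that: the primary endpoint counts onset from Day 71 in the double-blind phase, and the open-label efficacy summaries are descriptive. Nor do they show that the bias will occur, since Section 3 or the open-label SAP may set a later start. The correction is still worth making, because the protocol's own sentence points the wrong way.

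**What to change.** In 9.7.4, state that at-risk time for a 2-dose regimen starts no earlier than 14 days after dose 2, whatever calendar date is chosen. Add that any counted time and cases between dose 1 and dose 2 are assigned to 1-dose exposure, with regimen treated as time-varying. This matches the counting rule of the double-blind primary endpoint and, under equal incidence, brings the artefact to zero.

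The cost is one or two sentences and a matching line in the open-label SAP. Dose dates and case onset dates are already collected, so no extra participants, visits or samples are needed.

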9.8. Interim Analysis and Committees

The primary analysis of the double-blind phase will be performed after at least 90% of participants are unblinded at the and have moved from the double-blind phase to the open-label phase.

In addition to the current objectives and endpoints outlined for the double-blind analyses, the sponsor may conduct a preliminary and descriptive assessment of efficacy to assess the impact of the vaccine on possible emerging variants that may arise in the current epidemic situation. This analysis, if needed, will be performed by the independent statistical group that is supporting the IDMC of the trial (SSG). The sponsor personal directly involved in the oversight and conduct of the trial will be kept blinded. The results can only be shared with the Sponsor Committee and regulatory authorities upon request.

The study will be formally monitored by an IDMC. In general, the IDMC will monitor safety data on a regular basis to ensure the continuing safety of the participants. Enrollment will not be paused during these safety reviews, except after Stage 1 (approximately 1,000 participants). The IDMC will review unblinded data. The IDMC responsibilities, authorities, and procedures will be documented in the IDMC Charter.

Continuous monitoring for vaccine-associated enhanced disease will be performed through the SSG who will look at each of the diagnosed FAS COVID-19 events. Vaccine harm monitoring will be performed for severe/critical COVID-19/death endpoint based on the FAS. As these events will be monitored in real-time, and, after each confirmed respective case, the SSG will assess if a stopping boundary is reached. Specifically, monitoring for a higher rate of severe/critical disease or death in the vaccine group compared to the placebo group starts at the 5th event and at each additional event until the harm boundary is reached or until the primary analysis is triggered. If the stopping boundary is met, then the SSG immediately informs the Chair of the IDMC through secure communication procedures. At this point the IDMC will convene and provide a recommendation to the Sponsor Committee. As such, the potential harm monitoring is in real-time, resulting in the earliest indication of harm possible as soon as data come in; for more details , see Section 9.4.1 and 9.4.1.1

The monitoring rules will be detailed in the IDMC charter, with the statistical details in the SAP.

The SAP will describe the planned analyses in greater detail.

9.9. Analyses for cohort unblinded due to administration of an authorized/licensed COVID-19 vaccine

Investigators may receive requests to unblind study participants who become eligible to receive another authorized/licensed COVID-19 vaccine outside of the study if/when these become available. In these cases, the investigator will discuss with the participant available options and ramifications, including whether they are eligible to receive the Ad26.COV2.S vaccine in the study during the unblinding study visit. If the participant is eligible for an authorized/licensed vaccine according to local immunization guidelines or recommendation and if the participant wishes to proceed with the unblinding to receive another authorized/licensed COVID-19 vaccine outside of the study, the investigator will follow the unblinding procedures. The reason for the unblinding request should be documented.

When unblinding, if it is determined that the participant received the Ad26.COV2.S vaccine (and not placebo), the participant will be informed that there are no data on the safety of receiving 2 different COVID-19 vaccines. Unblinded participants will be asked to continue to be followed in this study in line with the [Schedules of Activities](#). Safety, efficacy and immunogenicity evaluations will be identical for all participants, if applicable and feasible, including participants that are unblinded to obtain an authorized/licensed COVID-19 vaccine and who remain in the study, including participants in the safety subset, if applicable and feasible. All data will be analyzed separately from the point of unblinding for safety, efficacy and immunogenicity, as described in the Statistical Analysis Plan.

